**CONFIDENTIAL** 

For the urine albumin and urine creatinine electrolyte, which are used to calculate the UACR, the corresponding LLOQ and ULOQ are:

Urine albumin:

- LLOQ (SI units): 3.0 mg/L

- ULOQ (SI units): 12800.0 mg/L

Urine creatinine:

- LLOQ (SI units): 0.100 mmol/L

- ULOQ (SI units): 11264.000 mmol/L

Established conversion factors will be used when conversion of measurement units is necessary.

# Partial or missing dates

Any AEs with incomplete start and end dates will be treated as follows:

- AEs with completely unknown start dates will be imputed with the date of first dosing, unless the imputed end date is known and prior to first dosing; in that case the start date will be imputed as the date of Screening.
- AEs with partially known start and end dates will be treated as follows:
  - o If only the day is missing, then the day will be imputed with the first day of the month, unless the month and year in which the AE started is a month and year in which IMP was administered, then the day will be imputed with the first day on which IMP was administered in that month. If in the case of start date this results in a start date after the imputed end date, then the day will be imputed with the first day of the month.
  - o If only the month is missing and the year is a year in which IMP was administered, then the month will be imputed with the first month in which IMP was administered. If in the case of start date this results in a start date after the imputed end date of the AE, then the month will be imputed with JAN. If the known year part is not a year in which IMP was administered, then the month will also be imputed with JAN.
  - o If both the day and month is missing and the year is a year in which IMP was administered, then the day and month will be imputed with the day and month of dosing. If in the case of start date this results in a start date after imputed end date, then the day and month will be imputed with 01JAN. If the year is not a year in which IMP was administered, then the day and month will also be imputed with 01JAN.
  - If only the year is missing, then the year will be imputed with the year of dosing.

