#### 4.11.2 Adverse Events

All AEs will be recorded from the time of randomisation and SAEs will be recorded from the time of signing the full ICF for the study (Visit 1a). No AE or SAE information will be collected after just signing of the optional pre-screening ICF. Recording of all AEs will continue until the end of the participant's safety follow-up period.

All AEs will be coded using the most recent version of the MedDRA that will have been released for execution at AstraZeneca or designee.

When not otherwise specified only AEs occurring with an onset date, or worsening, on or after first dose of investigational medical product (IMP) and within 28 days after last dose of IMP will be summarized.

The following rules will be used to determine whether or not an AE has taken place on-treatment:

- 1. An AE with an onset date and time on or after the date and time of first dose up to and including 5 days following the date and time of last dose of study treatment will be considered on-treatment
- 2. An AE with an incomplete start date and whose end date is not prior to the time of dosing on Day 1 will be considered to have taken place on-treatment unless the non-missing components of the incomplete start date indicate that the start date falls outside the time from dosing on Day 1 to last dose plus 5 days

The following variables will be collected for each AE:

- Adverse event diagnosis/description (verbatim)
- The date and time when the AE started and stopped
- Maximum intensity
- Whether the AE is serious or not
- Investigator causality rating against the investigational medicinal product AZD9977 and/or the investigational product Dapagliflozin (yes or no)
- Action taken with regard to investigational products (AZD9977 and/or Dapagliflozin)
- Adverse event caused subject's withdrawal from the study (yes or no)
- Outcome

Unless otherwise specified, all summaries will be provided by treatment group for the SS.

The number and percentage of AEs will be presented by SOC and/or PT and for each eGFR category.

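### SAP 4.4 imputes partial AE end dates early, so an end can precede a known start, and an event with an unknown start can be moved to Screening and out of the default AE tables

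*SAP*

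**What the plan says.** The rules are in SAP 4.4, under Partial or missing dates. They open with "AEs with partially known start and end dates will be treated as follows", and no separate rule for end dates follows.

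- **Day missing.** "If only the day is missing, then the day will be imputed with the first day of the month", with an exception: "unless the month and year in which the AE started is a month and year in which IMP was administered". In that case the first IMP day of the month is used.
- **Month missing, in a dosing year.** "then the month will be imputed with the first month in which IMP was administered".
- **Day and month missing, in a dosing year.** The day and month of dosing are used.
- **Order check.** "If in the case of start date this results in a start date after the imputed end date", the start is moved earlier. Nothing moves an imputed end later.
- **Start completely unknown.** The first dosing date is used by default. The exception reads "unless the imputed end date is known and prior to first dosing; in that case the start date will be imputed"; Screening is then the value used.

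SAP 4.11.2 then decides what is tabulated. By default, summaries include AEs with onset or worsening from first dose to 28 days after last dose. A separate on-treatment definition runs to 5 days after last dose. Its second rule keeps an AE with an incomplete start date if the end date is not before Day 1 dosing. The same section says "All AEs will be recorded from the time of randomisation", while SAEs are recorded from full consent at Visit 1a.

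**The concern.** Choosing an early date is cautious for a start, because it tends to pull an event of uncertain onset towards first dose. For an end date it works the other way, because it makes the event appear to finish sooner than it may have done. Two things follow if the rule is programmed as written.

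First, an imputed end can fall before a start that is fully recorded, because the order check protects only against a late imputed start.

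Second, the imputed end feeds the start date. With an unknown start, an end pushed before first dose triggers the clause under which "in that case the start date will be imputed as the date of Screening". The event then has a pre-treatment onset and drops out of the default AE tables, even if it truly ended on treatment. For a non-serious AE the result is also inconsistent with the collection window, since such events are recorded only from randomisation. Safety is a stated purpose of the study, so a rule that can remove an on-treatment event from the main tables should be corrected even if it seldom applies.

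**Working it through.** The documents give no figure to reproduce; the check traces the written rules.

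**Inputs.** From SAP 4.4: the day, month and unknown-start rules above. From SAP 4.11.2: the tabulation windows. From SAP 3.1: once-daily dosing for 12 weeks. Assumed for illustration: first dose on each of 1 to 31 March 2022 and 84 (12 × 7) consecutive daily doses, giving 31 × 84 = 2604 combinations of first-dose day and event day.

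The day-missing exception is keyed to the month in which the AE *started*. Applied to an end date, it can be read literally (start month) or leniently (month of the end date itself). Both readings were traced.

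**A. Known start, end in the same month, day missing.** First dose 15 March, start 20 March: March is a dosing month, so the end becomes 15 March, 5 days before the start. Both readings agree because the two months coincide.

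The imputed end avoids preceding the start only when the AE starts on the first IMP day of its month. First doses on 1 to 9 March give dosing in 3 calendar months; those on 10 to 31 March give dosing in 4.

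- Unaffected: 9 × 3 + 22 × 4 = 115
- Affected: 2604 − 115 = 2489, or 2489/2604 = 95.6%, by up to 30 days

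**B. Start completely unknown, end in the first-dose month, day missing.**

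| Reading of the exception | Imputed end | Start moved to Screening |
|---|---|---|
| Literal: start month unknown, so the exception cannot apply | 1 March | 30 of 31 first-dose days (all but 1 March) |
| Lenient: end month is a dosing month | first-dose day | 0 of 31 |

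**C. Start completely unknown, end month missing, day known.** The month becomes March whatever the true month was, and the exception plays no part. First dose 20 March, true end 15 April: imputed end 15 March, before first dose, so the start becomes Screening.

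For first dose on day d of March, the affected ends are those whose day of the month is below d: d − 1 in April, d − 1 in May, and d − 9 in June when d ≥ 10. Summed over d = 1 to 31:

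- April 465 + May 465 + June 253 = 1183
- 1183/2604 = 45.4%

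**Patterns that do not trigger Screening.** A day-missing end in a later dosing month becomes the 1st of that month, which is after first dose. An end with day and month both missing is set to the dosing date.

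**After the fix.** With day-missing ends set to the last day of the month, A falls to 0/2604 and B to 0/31. For C, the latest date consistent with the known parts cannot be earlier than the true end, so an event that truly ended after first dose cannot be imputed to end before it.

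These percentages are shares of date combinations. They do not estimate how often such records will occur.

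**The case against.** A fair defence has several parts.

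- **The rule does not always choose the earliest date.** A reader might infer that it does, but the exception can give the first IMP day, and a date with both day and month missing goes to the dosing date. This stands, and it removes some patterns, though not A or C.
- **Case B depends on wording.** If the exception is keyed to the month of the date being imputed, no event is lost in B. This stands: B is an ambiguity to settle. Case C does not rely on it.
- **Case A changes no table.** The AE summaries in SAP 4.11.2 use incidence, counts, intensity, outcome and time to first onset; none uses duration. With a known start, the onset is unchanged. This stands.
- **The event may survive elsewhere.** The second on-treatment rule could keep it if applied to the raw end date, and the AE listing covers every individual AE in the Safety Set. The listing point stands. The on-treatment point is uncertain, because the SAP does not say whether raw or imputed dates are used. Neither restores the event to the default 28-day tables, which rest on onset.
- **The Screening clause has a proper use.** SAEs are collected from Visit 1a, so one with an unknown start and an end before dosing can be genuinely pre-treatment. This stands for SAEs only.
- **Such records should be uncommon.** Start and stop dates are collected for each AE (Protocol 8.3.2), and AEs are reviewed at every visit from Visit 3 to Visit 11 (Protocol 1.3). This is reasonable and limits the size of the problem.

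**Conclusion.** The point holds as a specification error of small expected effect. A shared early-date rule can place an end before a known start, which is a listing error only. With a completely unknown start, it can also move an event to Screening and out of the default AE tables. That happens with a month-missing end whichever way the exception is read, and with a day-missing end in the first-dose month if the exception is read literally.

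A reader might go further and infer that partial end dates in general remove events, or that the safety tables will be materially understated. The documents do not support either. Loss from the tables needs a completely unknown start together with one of these two end-date patterns. The documents give no rate of incomplete dates; that the records will be few is a judgement. The primary UACR analysis does not use these dates.

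The conclusion assumes that the rules are programmed as written. The counts also assume uninterrupted daily dosing within one calendar year.

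**What to change.** Revise SAP 4.4, under Partial or missing dates, before database lock:

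1. Give end dates their own rule: impute a partial AE end date to the latest date consistent with its known parts, capped at end of follow-up or death.
2. Restrict the existing partial-date rule to start dates.
3. Allow a Screening start only for SAEs, and impute no non-serious AE start before randomisation.

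It would also help to state in SAP 4.11.2 whether the second on-treatment rule uses raw or imputed end dates.

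The cost is a few sentences and a small programming change. SAP 1 already provides for changes before database lock through a new SAP version. No extra data are needed.

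### Read literally, the AE partial-date rules date an ongoing second-year event about 9 to 12 months late when dosing spans New Year, putting it outside the default 28-day AE tables

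*SAP*

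**What the plan says.** SAP Section 4.4, under partial or missing dates, treats AE start and end dates by which component is missing.

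- **Day missing:** if the reported month and year include dosing, "then the day will be imputed with the first day on which IMP was administered in that month". This rule is tied to the reported month.
- **Month missing**, year is one in which IMP was given: "then the month will be imputed with the first month in which IMP was administered".
- **Day and month missing**, same condition on the year: "then the day and month will be imputed with the day and month of dosing".
- **Guard:** if the imputation "results in a start date after imputed end date, then the day and month will be imputed with 01JAN". The month-missing rule has a matching reset to January.
- **Year missing:** "If only the year is missing, then the year will be imputed with the year of dosing". No guard is attached.

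SAP Section 4.11.2 sets the default AE tables: onset or worsening on or after first dose, and "within 28 days after last dose of IMP will be summarized". It also defines a narrower on-treatment period, to last dose plus 5 days. There, inclusion is the default when the start date is incomplete: an event "whose end date is not prior to the time of dosing on Day 1 will be considered to have taken place on-treatment". The sole exception rests on what is known of the date and ignores the imputed one. It applies only when "non-missing components of the incomplete start date indicate that the start date falls outside the time from dosing on Day 1" until 5 days after last dose. The 28-day window has no such provision.

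**The concern.** The rules are evidently meant to count an onset of unknown timing from first dose: a wholly unknown start date is set to the first dosing date. The month-missing and day-and-month-missing rules do this only if the first dose falls in the reported year. If dosing began in October to December and the AE is reported with the following year, pasting the first-dose month onto that year gives a date long after treatment ended.

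At stake are the default counts of AEs and SAEs. Affected events leave those tables, so the error undercounts. The SAP would also contradict itself, placing the same event inside the period ending 5 days after last dose and outside the one ending 28 days after.

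**Working it through.** The documents give no figure on this point, so there is none to reproduce.

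**Inputs.** Twelve weeks of treatment (SAP Section 3.1), taken as 84 daily doses, so last dose = first dose + 83 days. The default AE window ends at first dose + 83 + 28 = first dose + 111 days, giving 112 possible onset days. Run-in dapagliflozin is not IMP (Protocol Table 5 footnote), so the first IMP dose opens the treatment phase. First-dose dates spread evenly over a 365-day year are an assumption.

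**One participant.** First dose 15 Nov 2021, last dose 6 Feb 2022, window to 6 Mar 2022, true onset 20 Jan 2022, literal reading of the rules:

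| Start as reported | End date | Imputed start | Error (days) | In 28-day window |
|---|---|---|---|---|
| 2022 only | ongoing | 15 Nov 2022 | +299 | no |
| 2022 only | 2022 only | 15 Nov 2022 (both dates) | +299 | no |
| 2022 only | 30 Jan 2022 | 1 Jan 2022 (guard) | −19 | yes |
| day 20, 2022 | ongoing | 20 Nov 2022 | +304 | no |
| day 20, 2022 | 30 Jan 2022 | 20 Jan 2022 (guard) | 0 | yes |
| 20 Jan, year missing (first-dose year used) | any | 20 Jan 2021 | −365 | no |

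In the second row the imputed start equals the imputed end, so it is not after it and the guard does not fire.

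**General size of the error.** With day and month missing, a second-year onset j days after first dose (1 to 83) is imputed at first dose + 365. The error is 365 − j, that is 282 to 364 days. The imputed date is always 365 − 83 = 282 days after last dose. With only the month missing, a first-dose month of October to December replaces an onset month of January to March. The error is 9, 10 or 11 calendar months (273 to 334 days). With no end date, every such AE falls outside the window. With an end date 14 days after onset (assumption), the guard fires, the start is 0 to 82 days early, and none falls outside.

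**How often the conditions arise.**
- Dosing spans New Year for first doses from 10 Oct to 31 Dec: 83/365 = 22.7% of participants.
- In these, second-year onset days within the window total the sum over m = 1 to 83 of (m + 28) = 3,486 + 2,324 = 5,810. All onset days: 365 × 112 = 40,880. So 5,810/40,880 = 14.2% of ongoing AEs lacking day and month are misplaced. For onsets on dosing days only it is 3,486/(365 × 84) = 11.4%.
- Year missing, first-dose year used: (111 × 112)/2 = 6,216 onset days, and 6,216/40,880 = 15.2%, whatever the end date.
- If 0.5 to 2% of AEs carry such dates (assumption): 0.5% × 14.2% = 0.07%, and 2% × 15.2% = 0.30%.

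**On-treatment status.** The narrower rule looks only at the known components. A start of 2022 does not show onset outside 15 Nov 2021 to 11 Feb 2022, so the event stays on-treatment. The same holds for every dosing-day onset checked.

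**A neighbouring case.** With only the month missing, a known day earlier than the first-dose day puts the imputed start before first dose even without a New Year crossing (about 44% of onset days in courses within one year). This is not in the figures above, but the corrected rule should cover it.

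**The case against.** The strongest reply is that the wording permits a harmless reading. The day-and-month rule does not say first dosing, and the month rule opens with the reported year, so both could mean dosing within that year. On that reading no second-year AE leaves the window, with or without an end date. This stands as a possible reading, but the SAP does not state it. The day-only rule states its own anchor, and the other two do not. It also does not help the year-missing rule, which has two candidate values when dosing spans New Year.

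The triggering records should also be rare. Protocol Section 8.3.2 collects AE start and stop dates and times, Section 8.3.4 asks about problems since the last visit, and post-randomisation visits are nominally at most 28 days apart. That stands, and it limits the size.

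A reader might infer something stronger: that dosing across New Year removes on-treatment AEs from the AE tables generally. The documents do not support that. First-year onsets are not touched by the New Year fault. The January reset normally rescues month-missing and day-and-month-missing AEs that have a usable end date. The on-treatment rule keeps the affected events in on-treatment summaries, and the hypotension preferred-term tables are planned under both definitions (SAP Section 4.11.3). The Safety Set listing covers each individual AE.

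**Conclusion.** The point holds in a limited form. Read literally, SAP Section 4.4 dates some AEs about 9 to 12 months late and removes them from the default 28-day tables. All of these must apply: dosing spans New Year, onset is in the second dosing year, the month or the day and month are missing, and the event is ongoing or its end date is equally incomplete. Such events remain on-treatment, so the SAP would count them in the narrower period but not the wider one. Separately, taking the first-dose year for a missing year dates a second-year AE 365 days early, whatever its end date.

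The effect is small. The documents do not give the frequency of such dates. About 0.1 to 0.3% of AEs is a ceiling for the New Year fault under an assumed 0.5 to 2% and even accrual, because it treats every partially dated AE as ongoing or as lacking only its year. Start dates concentrated in October to December would raise the 14.2% and 15.2%. Crossing New Year is realistic here: the protocol amendment of 20 December 2021 refers to patients already randomised.

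**What to change.** In SAP Sections 4.4 and 4.11.2:

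1. Month missing, or day and month missing, in a year in which IMP was given: impute the later of the first IMP date and the earliest date consistent with the known components. Keep the existing reset to January or 01JAN when the imputed start is after the end date. It is still needed, for example, for a serious event in run-in that ended before first dose. Where a known day would put the start before first dose, the first IMP date takes precedence.
2. Year missing: impute the year that places the date within first dose to last dose + 28 days and not after the end date; if none does, use the year of first dose. The window is 112 days, so at most one year can qualify.
3. Apply the incomplete-date logic of the on-treatment rule to the 28-day window as well.

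Anchoring to the reported year leaves second-year dosing-day onsets with month, or day and month, missing 0 to 82 days early and none outside the window. The cost is a few sentences in the SAP and a small change to the date-imputation program; no new data are needed.

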#### 4.5 **Populations for Analyses**

The following populations are defined.

TP-GDO-WW-016-08 **CONFIDENTIAL** Effective Date: 26 Nov 19 Project Document Effective Date: Date of last signature Related to: SOP-GDO-WW-019

**Table 1 Populations for Analyses** 

Population/Analysis Set	Description
Enrolled	All participants who sign the main ICF
Cohort 1 (randomized patients)	All participants randomized according to CSP versions 1.0 to 5.0
Cohort 2 (randomized patients)	All participants randomized according to CSP version 7.0
Full Analysis Set (FAS)	All participants who are randomised and either receive or do not receive any study intervention. Participants are evaluated according to the treatment assigned at randomisation. The FAS will be used for all analyses of demographic baseline characteristics and efficacy data.
Per Protocol Set (PPS)	A subset of the FAS consisting of all participants who do not violate the terms of the protocol in a way that may affect the primary efficacy endpoint significantly. All decisions to exclude participants from the per protocol analysis set will be made and documented prior to the unblinding of the study.
Safety set (SS)	All participants who are randomised and receive any study intervention. Participants are evaluated according to the actual treatment they received. If a participant received a different treatment dose than randomised throughout the study, they will be analysed according to the treated dose, not the randomisation dose. If a participant received study drug from the wrong kit for only part of the treatment duration, they will be analysed according to their randomisation dose.  The SS will be used for all safety analyses.
Pharmacokinetic set (PK)	All participants in the SS who have at least one quantifiable AZD9977 and/or dapagliflozin plasma concentration measurement after study start. The Pharmacokinetic Analysis set will be used for all pharmacokinetic assessments.
Pharmacodynamic set (PD)	All participants in the SS who have at least one quantifiable PD measurement after study start.  The Pharmacodynamic Analysis set will be used for all pharmacodynamic assessments.

Upon database release, protocol deviation and the analyses population will be produced for review. An analysis set classification meeting will be arranged to discuss the outputs and to decide which subjects and/or subject data will be excluded from certain analyses. Decisions made regarding the exclusion of subjects and/or subject data from analyses will be made prior to unblinding and will be documented and approved by the sponsor.

TP-GDO-WW-016-08 Effective Date: 26 Nov 19 Related to: SOP-GDO-WW-019

**Project Document Effective Date**: Date of last signature
Page 17 of 50

A summary of the number and percentage of participants in each analysis set will be provided by treatment group and overall. Exclusions from each analysis population will also be summarised overall and by reason.

By-participant listings of participants excluded from each analysis set and the data excluded from the FAS, the PPS, the SS, the PK and the PD will be provided.

